7 STUDY DESIGN

This study is designed as a prospective, comparative, sequential, non-randomized, multi-center, controlled clinical investigation.

There will be 4 centers worldwide that will recruit a total of 88 Subjects (44 Treatment Subjects and 44 Control Subjects). A complete description of the methods for determining sample size is contained in Section 10.9. Initially, the Subjects will be evenly distributed across the four sites; therefore it is expected that each site will recruit 22 Subjects (11 Control followed sequentially by 11 Treatment Subjects). In between the Control and Treatment Subjects, a learning curve is permitted for the use of SUI.

- The **Control group** will consist of 44 Subjects, 11 per site and the surgical procedure for these Subjects will be performed using Reusable Instruments (RUI).
- The **Treatment group** will consist of 44 Subjects, 11 per site and the surgical procedure for these Subjects will be performed using Single Use Instruments (SUI).

At each site the 11 Control Subjects will be enrolled and operated on prior to performing the first surgery in the Treatment group. For a given site, either Cruciate Retaining or Posterior Stabilising configurations will be used; consistent with their standard of care. Within a given CR site, the Investigator may choose to implant either the CR FB or CR RP. Similarly, within a given PS site, the Investigator may choose to implant either the PS FB or PS RP. Randomization is not being applied in this study in order to isolate and learn if there are changes in OR efficiency with SUI under normal operating room procedures.

One surgeon at each site will complete all RUI and SUI surgical cases including the learning curve. No Sub-Investigators will be permitted to perform surgery to avoid possible confounding issues with varying surgical process. All sites will have previously completed their learning curve with the ATTUNE Primary Implant implanted using RUI prior to enrolling the 1st patient. Then after the completion of all RUI study cases, a learning curve will be permitted for the use of SUI. The duration of the SUI learning curve is anticipated to be approximately 5 cases and is at the discretion of the Principal Investigator. These early cases that are within the learning curve will not be enrolled into this study at each site.

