Both resurfaced patellae and non-resurfaced patellae are permitted in this investigation, consistent with site standard of care. TruMatch technology or any other type of Custom Patient Instruments are not permitted. Similarly Computer-Assisted Surgery (CAS) is not permitted within the study. The procedures must be performed using only the instrumentation provided (SUI or RUI) and standard surgical methods, without additional tools that could confound the key research question of this study (for example, instrumentation that helps perform bone resections).

The Sponsor will monitor overall project enrollment. Cohort reallocation during the RUI phase only may be done in order to maintain project timelines. The Sponsor can authorize a shift of a group of Subjects from one site to another to maintain project timelines. For example, the Sponsor can reduce the cohort of a slow-enrolling RUI site to a faster-enrolling RUI site and the faster-enrolling RUI site will assume responsibility for the reallocated RUI cohort and the same number of SUI Subjects.

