# 1 Study Design

This study is designed as a prospective, comparative, sequential, non-randomized, multi-center, controlled clinical investigation. Randomization will not be utilized in this study in order to isolate and learn if there are changes in Operating Room (OR) efficiency with Single-Use Instrumentation under normal operating room procedures.

There will be 4 centers worldwide that will recruit a total of 88 Subjects: 44 treatment [Single-Use Instrumentation, (SUI)] and 44 control [Reusable Instrumentation, (RUI)]. A complete description of the methods for determining sample size is contained in Section [7](#). The recruitment goal will be to evenly distribute enrollment across the four sites; therefore, it is expected that each site will enroll 22 Subjects (11 Control followed sequentially by 11 Treatment Subjects).

- The **Control group** will consist of 44 Subjects, 11 per site and the surgical procedure for these Subjects will be performed using Reusable Instruments (RUI).
- The **Treatment group** will consist of 44 Subjects, 11 per site and the surgical procedure for these Subjects will be performed using Single Use Instruments (SUI).

For a given site, either Cruciate Retaining (CR) or Posterior Stabilizing (PS) configurations will be used; consistent with their standard of care. Within a given CR site, the Investigator may choose to implant either the CR Fixed Bearing (FB) or CR Rotating Platform (RP) configurations. Similarly, within a given PS site, the Investigator may choose to implant either the PS FB or PS RP configurations.

One surgeon at each site will complete all RUI and SUI surgical cases including the learning curve cases. No Sub-Investigators will be permitted to perform surgery to avoid possible confounding issues with varying surgical process. All sites will have previously completed their learning curve cases with the ATTUNE Primary Implant implanted using RUI prior to enrolling the first patient. Then after the completion of all RUI study cases, a series of learning curve cases will be permitted for the use of SUI. The duration of the SUI learning curve is anticipated to be approximately 5 cases and is at the discretion of the Principal Investigator. These early cases that are within the learning curve will not be enrolled into this study at each site.

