## 8 Analyses to be Conducted

### 8.1 General Conventions

Study data will be tabulated for all subjects in the target analysis population using SAS v9.3 or higher. Planned tabulations are described below and table, figure, and listing shells are provided separately (see [Appendix](#) for file name).

Standard descriptive summaries for continuous data include the number of subjects with nonmissing data (n), mean, SD, median, minimum, and maximum values. For categorical data, the count and percentage will be provided. Percentages will be based on the number of subjects without missing data.

When there is a need to test the significance of a difference between groupings of comparisons of SUI versus RUI which result in a p-value or confidence interval, a t-test will be conducted for continuous variables, and Fishers' Exact Test will be used for categorical variables.

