## **OR Efficiency**

Exploratory analyses will be conducted to see if SUI improves OR efficiency compared to conventional (RUI) instruments. Specifically, the following durations will be assessed comparatively between treatment groups and stratified by site:

- OR Set-up Time: Set-up Stop Time – Set-up Start Time;
- Anesthesia Time: Anesthesia Stop Time – Anesthesia Start Time;
- Surgery Time: Surgical Stop Time – Surgical Start Time;
- Clean-Down Time: Clean Down Stop Time – Clean Down Start Time;
- Total Time: Clean Down Stop Time – Set-up Start Time.

For each of the OR Efficiency endpoints defined above, analysis will be conducted by summarizing the endpoint as a continuous result (n, mean, SD, median, min, max, 95% CI) and presenting results by treatment group. In this analysis, 2 sample t-tests will be used to assess the difference in the mean response between treatment groups.

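### Operating-room times are to be compared stratified by site, but the only test named has no site term, so precision is given up whenever sites differ

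*SAP*

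**What the plan says.** SAP 8.4.3 (OR Efficiency) defines five durations: set-up, anesthesia, surgery, clean-down and total time. It states that "the following durations will be assessed comparatively between treatment groups and stratified by site". The analysis paragraph that follows plans "summarizing the endpoint as a continuous result (n, mean, SD, median, min, max, 95% CI) and presenting results by treatment group", and then "2 sample t-tests will be used to assess the difference in the mean response between treatment groups". SAP 8.1 gives the same general rule for comparing SUI with RUI: "a t-test will be conducted for continuous variables". Neither place names a stratum, a covariate or a confidence interval for the SUI minus RUI difference.

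On the design, SAP 1 plans four sites with 22 subjects each, 11 per arm, and "One surgeon at each site will complete all RUI and SUI surgical cases". If the sponsor moves part of a cohort between sites, Protocol 7 keeps the arms matched within site: "the faster-enrolling RUI site will assume responsibility for the reallocated RUI cohort and the same number of SUI Subjects". Protocol 10.10 also lists exploratory work on differences between sites in operating-room times. SAP 5 treats everything except the primary endpoint as exploratory and unpowered.

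**The concern.** Site is the obvious source of variation in these times. Each site is a different hospital with a different surgeon, and the protocol itself plans to look at how sites differ. The design balances arm within site, so between-site variation cancels out of the SUI minus RUI difference. A pooled two-sample t-test does not use this. It measures the spread within each arm across all four sites, so site differences inflate the standard error of a contrast they do not affect.

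This matters because operating-room efficiency is the stated reason for the non-randomized design: "Randomization is not being applied in this study in order to isolate and learn if there are changes in OR efficiency". The precision that the within-site balance offers should be used for that question. The wording also leaves the analyst to choose after seeing the data. Stratified by site could mean by-site tables, four separate 11 versus 11 tests, or one stratified or adjusted test.

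**Working it through.** **The plan's own power figure.** The only power statement in the documents is for the primary endpoint: 35 per group, SD 1.87°, margin 1.5°, one-sided alpha 0.05, 95% power. The noncentrality is 1.5 / (1.87 × √(2/35)) = 1.5 / 0.447 = 3.36. With 68 degrees of freedom the power is 95.3%, so the figure reproduces. There is no counterpart for operating-room times.

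**Inputs from the documents.** Four sites, 11 subjects per arm per site, 44 per arm, two-sided 95% intervals (SAP 1 and 5).

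**Assumptions.** The share ρ of the total variance in a duration that lies between sites is set at 0, 5, 10, 30 and 50%. Site effects are drawn at random from a normal distribution and are the same in both arms of a site. The total SD is 1 and the true difference is 0.5 SD.

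**Point estimate.** With equal numbers per arm in every site, each site effect enters both arm means with the same weight. The pooled and the site-adjusted differences are identical.

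**Standard error.** The site-adjusted model has 88 − 4 − 1 = 83 residual degrees of freedom and residual variance 1 − ρ. The pooled test has 88 − 2 = 86. Its expected variance is (1 − ρ) + (44/43) × (3/4) × ρ, because four sites vary around their own mean by 3/4 of the population variance on average. The ratio of interval widths is therefore approximately √[1 + (44/43) × 0.75 × ρ/(1 − ρ)]:

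- ρ = 5%: √(1 + 0.767 × 0.0526) = 1.02
- ρ = 10%: √(1 + 0.767 × 0.111) = 1.04
- ρ = 30%: √(1 + 0.767 × 0.429) = 1.15
- ρ = 50%: √(1 + 0.767 × 1) = 1.33

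Simulation gives the same values except 1.31 at 50%. The formula takes the root of an average, which lies slightly above the average of the roots.

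**Power of the adjusted model.** The noncentrality is 0.5 / (√(1 − ρ) × √(2/44)) = 2.345 / √(1 − ρ), which is 2.35, 2.41, 2.47, 2.80 and 3.32 for the five shares. The power of the pooled test comes from simulation.

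| Between-site share (assumed) | Pooled interval wider by | Power, pooled t-test | Power, arm + site |
|---|---|---|---|
| 0% | 0% | 64% | 64% |
| 5% | 2% | 65% | 66% |
| 10% | 4% | 66% | 69% |
| 30% | 15% | 70% | 79% |
| 50% | 31% | 74% | 91% |

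The simulated type I error of the pooled test at 10, 30 and 50% is about 4.2, 2.8 and 1.6%, against a nominal 5%.

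**Sensitivity.** If the four sites are instead fixed so that their spread equals the stated share exactly, the factor 3/4 drops out. The interval is then 3, 6, 20 and 42% wider at 5, 10, 30 and 50%. With fixed sites, a 20% share and an uneven split that is still 1:1 within site (16, 11, 11 and 6 per arm), it is 11% wider. If stratified meant four separate 11 versus 11 tests, each would have about 27% power for an effect (0.604 within-site SD) that 44 versus 44 detects with 80% power when sites do not differ.

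**The case against.** The strongest reply is that site is in the plan. The section says the comparison is stratified, and Protocol 10.10 covers differences between sites. A pooled test accompanied by by-site tables would satisfy both sentences, and the table shells that might settle this are in a separate document. This stands in part. A reader might infer that the SAP contradicts itself or disregards site, and the text does not go that far. What it shows is that the one test named does not carry out the stratification announced just before it.

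A reader might also infer that the planned intervals are wrong. The 95% interval in this section is listed among the by-group summaries, and none is specified for the difference. The extra width applies to the interval that the t-test implies. That interval covers at least as often as it claims.

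Nor does the trial miss a power target here, since SAP 5 sets none for these endpoints. On the scale of total SD, the pooled test never falls below the 64% it has when sites do not differ. What is given up is a gain, not a promised level. Protocol Table 10-2 lists no difference as the expected result for efficiency, but it is a column of expectations and not a test criterion. It does not show that a null result was built in.

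Two further points stand. Exact balance is planned but not assured, because SAP 6.2 assigns mixed-instrument cases in the Safety Set according to the instruments used. And all RUI cases precede all SUI cases at each site, so arm is confounded with calendar period. A site term leaves that untouched, and a narrower interval around the same difference could look more certain than it is.

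**Conclusion.** The point holds as a minor, inexpensive improvement. The named test leaves out the stated stratification, and under the planned within-site balance it is valid but conservative whenever sites differ. The loss depends on a between-site share of variance that the documents do not give. It is negligible at 0 to 5%. At 30 to 50% it becomes material: intervals 15 to 31% wider, and 9 to 17 points of power not gained at 0.5 SD. The figures assume additive, normally distributed site effects and 11 subjects per arm per site. No primary result, decision rule or stated power figure is affected.

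**What to change.** In SAP 8.4.3, for the five durations, replace the two-sample t-test with a linear model containing arm and site. Report the site-adjusted SUI minus RUI difference with its two-sided 95% confidence interval. Keep the by-site results descriptive, so that the meaning of stratified by site is settled before the data are analyzed. Add one sentence saying that site adjustment does not remove the confounding of arm with calendar period in the sequential design.

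The cost is a few lines of SAP text, a matching change to the table shells where needed, and three residual degrees of freedom (86 to 83). No new data are required. If sites turn out not to differ, the result is practically unchanged. If numbers within a site end up slightly unequal, the model also corrects the point estimate for that imbalance.

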### **Procedural Delays**

The incidence of procedural obstacles (i.e., Staff change-over, Holes in blue wrap, Late staff, Missing instrument(s), Missing implants, Patient delay, Prolonged anesthesia, Prolonged surgery, Scrub nurse not familiar with instruments, or Other) will be summarized for both treatment groups.

For each site (surgeon), a listing of procedural obstacles will be generated which presents the procedural obstacles for the site's first through last case.

## **8.5 Safety Analyses**

For this study, only serious AEs and those AEs related or possibly related to either the device and/or the procedure are to be reported to the Sponsor (Please see Figure 9-1 in the CIP). AEs were collected from the time of surgery forward and coded by MedDRA v17.0.

An adverse event overview table will be provided and will include both the number of events (n) and the number and percentage (n, %) of subjects with 1 or more event in the following categories:

- Serious,
- Definitely, probably, or possibly device-related,
- Definitely, probably, or possibly procedure-related,
- Operative site,
- Systemic,
- Intra-operative (AE with onset on the day of surgery), and
- Post-operative (AE with onset after the date of surgery).

In addition, all adverse events will be listed.

#### **8.6 Handling of Missing Data**

No missing data methods will be implemented to account for missing data.

#### **8.7 Sensitivity Analyses**

The analysis of the primary endpoint will be repeated using all subjects in the Safety Population with available data to determine the robustness of the study outcome.

### **9 Data Monitoring Committee (DMC)**

No DMC is required for this study.

## **Appendix: Tables, Listings and Graphs Shells**

The document that contains the tables, listings and graphs shells is entitled Study 10002 Table Figure and Listing Shells.

End of Document
